7.6. Criteria for Study Termination

The Sponsor may suspend or terminate the study, or part of the study, at any time for any reason including, but not limited to, safety and lack of efficacy

If the Sponsor, investigator, or regulatory agency officials discover conditions arising during the study that indicates that the study should be halt d or that a study site should be closed, this action may be taken after appropriate consul ation between the Sponsor, its designee, and the site investigator. If the study is suspended or terminated, the Sponsor or its designee will ensure that applicable sites, regulatory health authorities, and IRBs/ECs are notified as appropriate.

Protocol EBS-101-TD-301 Version 9.0, 05 March 2024

Table 3: Schedule of Assessments

| | | | Open-Label | Stabilizatio | n Period | | | | | | | | | | | | |
|---|--|------------------------------|--|--|---------------------------------------|--|---------------------------------------|---------------------------------------|---|--|--|---|--|---|--------------------------------------|--|---|
| | Screening Period ^a | Titrati | on Phase | W | tenance Pleeks 4 to 1 y 29 up to 8 | 2 | | | Double-Bli | Week | mized Witho as 12 to 24 85 to 169) | rawal Perio | od | | | ifety Follo Days 170 | |
| Visit/TC Study Day | Screening VISIT 1 Day -28 to -1 | Baseline VISIT 2 Day 1 | W 2 f Day 15 Telephone call only (±3d) | W4 / VISIT 3/ Day 29 (±3d) | W8 / VISIT 4 / Day 57 (±3d) | W 12 VISIT 5 Day 85 (±3d) | W13 / VISIT 6 / Day 92 (±3d) | W14 / VISIT 7 / Day 99 (±3d) | W15 / VISIT 8 / Day 106 (±3d) | W1 / VISIT 9 / Day 113 (± d) | W18 / VISIT 10 / Day 127 (±3d) | W20 / VISIT 11 / Day 141 (±3d) | W22 / VISIT 12/ Day 155 (±3d) | W 24 VISIT 13 Day 169 or Relapse or ET (±3d) | 7 Day F/U VISIT 14 (±3d) | 14 Day F/U VISIT 15 (±3d) | 30 Day F/U ^f Telephone call only (±3d) |
| Informed Consent ^a | X | | | | | | | | 18 | | | | | | | | |
| DSM-5-TR Criteria for TD | X | | | | | | | | 7 |) | | | | | | | |
| Inclusion/ Exclusion | X | X | | | | | | | | | | | | | | | |
| Medical/Psychiatric / Medication History | X | X | | | | ~(| | | | | | | | | | | |
| Randomization | | | | 1 | | X | | | | | | | | | | | |
| Physical Exam/Vital Signs ^b | X | X | | X^b | X | X | X | X | X | X | X | X | X | X | X | X | |
| ECG ^b | X | X | | X | | X | | | | | X | | | X | X | X | |
| Central Laboratory tests (Hematology, Chemistry, Urinalysis, HbA1c, Prolactin) ^c | X | X | | | | X | | | | | X | | | X | X | X | |
| Central Urine Drug Screen | X | X | | X | X | X | X | X | X | X | X | X | X | X | X | X | |
| Local Urine Pregnancy Test ⁱ | X | X | | X | X | X | X | X | X | X | X | X | X | X | X | X | |
| Yale Global Tic Severity Scale | X | X | | X | X | X | X | X | X | X | X | X | X | X | X | | |

Confidential

Page 39 of 96

Protocol EBS-101-TD-301 Version 9.0, 05 March 2024

| | | | Open-Label | Stabilizatio | on Period | | | | | | | | | | | | |
|--|--|------------------------------|--|--|---|--|---------------------------------------|---------------------------------------|---|---|---|---|--|---|--------------------------------------|--|---|
| | Screening Period ^a | Titrati | ion Phase | W | tenance Pl eeks 4 to 1 y 29 up to 8 | 2 | | | Double-Bli | Week | mized Withous 12 to 24 85 to 169) | lrawal Perio | od | | | fety Follo Days 170 | |
| Visit/TC Study Day | Screening VISIT 1 Day -28 to -1 | Baseline VISIT 2 Day 1 | W 2 f Day 15 Telephone call only (±3d) | W4 / VISIT 3/ Day 29 (±3d) | W8 / VISIT 4 / Day 57 (±3d) | W 12 VISIT 5 Day 85 (±3d) | W13 / VISIT 6 / Day 92 (±3d) | W14 / VISIT 7 / Day 99 (±3d) | W15 / VISIT 8 / Day 106 (±3d) | W16 / VISIT 9 / Day 113 (±3d) | W18 / VISIT 10 / Day 127 (±3d) | W20 / VISIT 11 / Day 141 (±3d) | W22 / VISIT 12/ Day 155 (±3d) | W 24 VISIT 13 Day 169 or Relapse or ET (±3d) | 7 Day F/U VISIT 14 (±3d) | 14 Day F/U VISIT 15 (±3d) | 30 Day F/U ^f Telephone call only (±3d) |
| Clinical Global Impression – Tourette Syndrome Severity | X | X | | X | X | X | X | X | X | X | X | X | X | X | | | |
| Clinical Global Impression – Tourette Syndrome Improvement | | | | X | | X | X | X | X | X | X | X | X | X | | | |
| Caregiver Global Impression of Change ^h | | | | Х | | X | | | | | X | | | X | | | |
| Gilles de la Tourette Syndrome – Quality of Life Scale for Children and Adolescents ^h | | X | | 1 | | X | | | | | | | | X | | | |
| Gilles de la Tourette Syndrome – Quality of Life Scale ^g | | X | | | | X | | | | | | | | X | | | |
| Premonitory Urge for Tics Scale | | X | | X | | X | | | | | X | | | X | | | |
| Columbia Suicide Severity Rating Scale | X | X | X | X | X | X | X | X | X | X | X | X | X | X | X | X | |
| Children's Depression Rating Scale – Revised ^h | X | X | | X | X | X | X | X | X | X | | X | | X | | | |
| Pediatric Anxiety Rating Scale ^h | | X | | X | X | X | X | X | X | X | | X | | X | | | |

Confidential

Page 40 of 96

Protocol EBS-101-TD-301 Version 9.0, 05 March 2024

| | | | Open-Label | Stabilizatio | on Period | | | | | | | | | | | | |
|---|--|------------------------------|--|--|---------------------------------------|--|---------------------------------------|---------------------------------------|---|---|--|---|--|---|--------------------------------------|--|---|
| | Screening Period ^a | Titrati | on Phase | W | tenance Pleeks 4 to 1 y 29 up to 8 | 2 | | | Double-Bli | Week | mized Withd as 12 to 24 85 to 169) | lrawal Perio | od | | | fety Follo Days 170 | |
| Visit/TC Study Day | Screening VISIT 1 Day -28 to -1 | Baseline VISIT 2 Day 1 | W 2 f Day 15 Telephone call only (±3d) | W4 / VISIT 3/ Day 29 (±3d) | W8 / VISIT 4 / Day 57 (±3d) | W 12 VISIT 5 Day 85 (±3d) | W13 / VISIT 6 / Day 92 (±3d) | W14 / VISIT 7 / Day 99 (±3d) | W15 / VISIT 8 / Day 106 (±3d) | W16 / VISIT 9 / Day 113 (±3d) | W18 / VISIT 10 / Day 127 (±3d) | W20 / VISIT 11 / Day 141 (±3d) | W22 / VISIT 12/ Day 155 (±3d) | W 24 VISIT 13 Day 169 or Relapse or ET (±3d) | 7 Day F/U VISIT 14 (±3d) | 14 Day F/U VISIT 15 (±3d) | 30 Day F/U ^f Telephone call only (±3d) |
| Extrapyramidal Symptom Rating Scale | | X | | X | X | X | X | X | Х | X | X | X | X | X | | | |
| Swanson, Nolan, and Pelham Questionnaire-IV- 26 ^h | | X | | X | X | X | X | X | X | X | | X | | X | | | |
| Children's Yale- Brown Obsessive Compulsive Scale- II ^h | | X | | X | X | X | x | Х | X | X | | X | | X | | | |
| Patient Health Questionnaire-9g | X | X | | X | Х | X | Х | X | X | X | | X | | X | | | |
| Hamilton Rating Scale for Anxiety ^g | | X | | X | X | X | X | X | X | X | | X | | X | | | |
| Conners' Adult ADHD Rating Scale ^g | | X | | X | X | X | X | X | X | X | | X | | X | | | |
| Yale-Brown Obsessive Compulsive Scale- II ^g | | X | | X | X | X | X | X | X | X | | X | | X | | | |
| PK Blood Draws ^{d,e} | | | | X | X | X | | | | | | | | | | | |
| Adverse Events | X | X | X | X | X | X | X | X | X | X | X | X | X | X | X | X | X |
| Concomitant Medications | X | X | | X | X | X | X | X | X | X | X | X | X | X | X | X | |

Confidential

Page 41 of 96

Protocol EBS-101-TD-301 Version 9.0, 05 March 2024

| | | | Open-Label | Stabilizatio | on Period | | | | | | | | | | | | |
|--|--|------------------------------|--|--|---|--|---------------------------------------|---|---|---|---|---|--|---|--------------------------------------|--|---|
| | Screening Period ^a | Titrati | on Phase | W | Maintenance Phase Weeks 4 to 12 (Day 29 up to 84) | | | Double-Blind Randomized Withdrawal Period Weeks 12 to 24 (Days 85 to 169) | | | | | | | Safety Follow-Up (Days 170-199) | | |
| Visit/TC Study Day | Screening VISIT 1 Day -28 to -1 | Baseline VISIT 2 Day 1 | W 2 f Day 15 Telephone call only (±3d) | W4 / VISIT 3/ Day 29 (±3d) | W8 / VISIT 4 / Day 57 (±3d) | W 12 VISIT 5 Day 85 (±3d) | W13 / VISIT 6 / Day 92 (±3d) | W14 / VISIT 7 / Day 99 (±3d) | W15 / VISIT 8 / Day 106 (±3d) | W16 / VISIT 9 / Day 113 (±3d) | W18 / VISIT 10 / Day 127 (±3d) | W20 / VISIT 11 / Day 141 (±3d) | W22 / VISIT 12/ Day 155 (±3d) | W 24 VISIT 13 Day 169 or Relapse or ET (±3d) | 7 Day F/U VISIT 14 (±3d) | 14 Day F/U VISIT 15 (±3d) | 30 Day F/U ^f Telephone call only (±3d) |
| Dispense Study Drug | | X | | X^d | X | X | | | | X | | X | | X | | | |
| Collect Unused Study Drug/Assess Drug Compliance | | | | X | X | X | X | X | х | x | X | X | X | X | X | | |

Abbreviations: ADHD = attention-deficit hyperactivity disorder; AE = adverse event; BP = blood pressure; DSM-5-TR = Diagnostic and Statistical Manual of Mental Disorders, Fifth Edition; ECG = electrocardiogram; F/U = follow up; HR = heart rate; PK = pharmacokinetic(s); TD = Tourette's Disorder

Neurological exam should be part of the physical exam. Physical exam t Week 4 visit will include assessment for serotonin syndrome. If serotonin syndrome symptoms are present, local laboratory assessment should be performed.

Confidential

^a Informed consent must be obtained prior to any screening procedures. All screening procedures are to occur after confirmation of appropriate timeframe since discontinuation of applicable medications. Rescreening is allowed after approval by the Medical Advisor.

^b Vital signs will include pulse, BP (done 5 minutes after being supine) height and weight.

^c Subjects should be in a fasting state (8 hours) for laboratory t sts. Fas ing at the Screening visit is optional. HbA1c will be measured only at Baseline, Week 12, and Week 24 (completed subjects only).

d At Week 4, ecopipam should be administered after the pre-dose blood draw. PK samples will be collected at 1) pre-dose; 2), post-dose between 0.5 and 1.5 hours; and 3) post-dose between 2 and 4 hours. Week 12 PK assessment only to be performed if Week 8 assessment is missed.

^c If visits at Weeks 4, 8 and/or 12 are completed in locations other than study clinic due to restrictions because of the COVID-19 pandemic or other qualifying event, then collection of labs for PK assessments are optional.

f Week 2 and 30-Day FU visits will be a telephone call. If there are any abnormal findings, the subject will be brought to the site for full assessment. Subjects who complete the Baseline visit for the EBS-101-TD-391 open label extension study within 30 days of the Week 24 visit are not required to complete the 30-Day FU telephone call.

^g Administration applicable to adult subjects only.

^h Administration applicable to child and adolescent subjects only (6-17 years of age).

ⁱ For women of childbearing potential only. If positive, request a serum HCG on the Chemistry blood sample requisition form for confirmation of pregnancy.

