Safety will be assessed by monitor ng and recording all adverse events (AEs) and Serious Adverse Events (SAEs) at all Visits, regular monitoring of hematology, blood chemistry, urinalysis and prolactin (Screening, Basel n Weeks 12 and 18, Completion [Week 24] or Relapse/Early Termination, and 7- and 14-day Follow Up visits). HbA1c will be measured at Baseline, Week 12 and Completion Week 24 visits. Regular measurement of vital signs and the performance of a physical examination will occur at every visit. An ECG will be done at Screening, Baseline and Weeks 4, 12, 18, and 24 and at the 7-and 14-day Follow Up visits. An additional assessment will include the Columbia-Suicide Severity Rating Scale (C-SSRS) (all Visits except 30-day Follow up visit). Additional safety outcomes (occurring at specified visits at Baseline and Weeks 4, 8, 12, 13, 14, 15, 16, 18, 20, 22, and 24) will include the Children's Depression Rating Scale-Revised (CDRS-R) for children and adolescents, the Pediatric Anxiety Rating Scale (PARS), for children and adolescents, the Swanson, Nolan and Pelham (SNAP-IV-26) questionnaire for children and adolescents, the Children's Yale-Brown Obsessive-Compulsive Scale-II (CY-BOCS-II), the Conners Adult ADHD Rating Scale – Self Report: Short Version (CAARS-S:S) for adults, the Hamilton Rating Scale for Anxiety (HAM-A) for adults, the Patient Health Questionnaire-9 (PHQ-9) for adults, the Yale-Brown Obsessive-Compulsive Scale-II (Y-BOCS-II) for adults, and the Extrapyramidal Symptom Rating Scale (ESRS) for children, adolescents, and adults.

Protocol EBS-101-TD-301 Version 9.0, 05 March 2024

PK:

Blood samples will be collected to measure concentrations of ecopipam and its major (active) metabolites at Weeks 4 and 8. If the Week 8 PK assessment is missed, samples may be drawn at Week 12 during the open-label Stabilization period.

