12.1. Safety Parameters

Safety will be assessed by monitoring and recording all adverse events (AEs) and Serious Adverse Events (SAEs) at all Visits, regular monitoring of hematology, blood chemistry, urinalysis, and prolactin (Screening, Baseline, Week 12, Week 18 and Week 24 Completion or Relapse/Early Termination, and 7- and 14-day Follow Up visits). HbA1c will be measured at Baseline, Week 12 and at Week 24 Completion or Early Termination visits. Regular measurement of vital signs and the performance of a physical examination will occur at every visit. An ECG will be performed at Screening, Baseline and Weeks 4, 12, 18, and 24 after supine BP is collected and at the 7-day and 14-day Follow Up visits. All subjects will be monitored for signs or symptoms signs or symptoms of withdrawal, abuse and dependence.

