12.1.12. Electrocardiogram (ECG)

Sites will be provided with a 12-lead ECG device to complete assessments per Table 3. Clinicians will instruct subjects to follow-up with care as appropriate upon evidence of new or worsening abnormal ECG readings.

12.1.13. Central Laboratory Tests:

Subjects should be in fasting state (minimum of 8 hours) for all blood laboratory tests collected at study visits after the Screening visit, per Table 3.

| Category | Test names |
|-------------------|--|
| Hematology | Red blood cell (RBC) count, hemoglobin (Hb), hematocrit (Hct), platelets, and white blood cell (WBC) count with differential (neutrophils, bands lymphocytes, monocytes, eosinophils, basophils, immature granulocyte) Mean Corpuscular Hemoglobin (MCH), Mean Corpuscular Hemoglobin Concentration (MCHC), Mean Corpuscular Volume (MCV), Mean Platelet Volume (MPV), Red Cell Distribution Width (RDW), CBC, Nucleated Red Blood Cell |
| Chemistry | Glucose, calcium, albumin, cholesterol, triglycerides, phosphorus, lactate dehydrogenase (LDH), total protein, globulin, prolactin; Liver function tests: albumin, alkaline phosphatase (ALP), aspartate aminotransferase (AST/SGOT), alanine aminotransferase (ALT/SGPT), total bilirubin, direct bilirubin, Calcium (Ca), Total cholest rol, glucose, lactate dehydrogenase (LDH), phosphorous, total protein, triglycerides; Electrolytes: sodium (Na), potassium (K), chloride (Cl), bicarbonate; Renal function tests: Blood urea/blood urea nitrogen (BUN), creatinine |
| Urinalysis | Complete urinalysis includes color, appearance, specific gravity, pH, protein, glucose, ketones, and blood with microscopic examination for positive protein or blood results |
| Pregnancy Test | A local urine test (for women of childbearing potential only) and central laboratory serum test to confirm a positive urine result |
| Urine Drug Screen | Central laboratory test to detect the presence of cocaine, amphetamine, benzodiazepines, barbiturates, phencyclidine (PCP), opiates |
| Special Test | Hemoglobin A1c (HbA1c) at Baseline, Week 12 and Week 24 |

| Emalex Biosciences, Inc. | Protocol EBS-101-TD-301 |
|--------------------------|----------------------------|
| Ecopipam | Version 9.0, 05 March 2024 |

Maximum blood volume to be drawn at each visit is noted below.

| Visit | Maximum Blood Volume (mL) |
|-----------------------------|---------------------------|
| Visit 1 – Screening | 6 |
| Visit 2 – Baseline | 8 |
| Visit 3 – Week 4 | 14 |

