13.5. Sample Size Justifications

The planned number of Relapse events for the double-blind R/WD Phase is 49 children and adolescents. This number of events will provide 85% power to detect a difference between treatment groups, assuming a hazard ratio of 0.4 for Relapse and statistical testing at alpha level 0.05 (2-sided). Subject enrollment will stop around the time that 49 Relapse events among children and adolescents are expected to have occurred. The number of Relapses among adults will not determine study completion.

Assuming the proportion of subjects who Relapse in the DB randomization phase is 65% in the placebo group and 34% in the ecopipam group, approximately 98 subjects (49 subjects per group) will be required to achieve this number of events.

Total Number of Subjects:

Approximately 196 subjects (children and adolescents) will be enrolled into the open-label Stabilization Period in order to randomize 98 subjects age ≥ 6 to < 18 years of age assuming the stabilization rate in the open-label Stabilization Period is 50%. n addition, approximately 40 adult subjects are also expected to be enrolled.

Protocol EBS-101-TD-301 Version 9.0, 05 March 2024

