#### 12.2. Laboratory Evaluations

Blood samples for hematology, chemistry, prolactin and urine samples for urinalysis are to be collected at screening, Baseline, Weeks 12 and 18, Completion [Week 24] or Relapse/Early Termination and 7 day and 14 day Follow Up visits. All results will be provided using International System of Units (SI). HbA1c will be measured at the baseline, week 12 and week 24 completion or early termination visits.

Descriptive statistics for hematology, chemistry, prolactin and HbA1c will be provided for each test parameter and for change from baseline treatment by visit and for each treatment group. Shift tables (i.e., low-normal-high at Baseline versus low-normal-high at each post-baseline visit in a 3-by-3 contingency table) will be provided for hematology, chemistry, prolactin, HbA1c and urine to assess changes from Baseline in laboratory values by visit for each treatment group. Shift (0.5% change) from baseline will be summarized for HbA1c by visit for each treatment group.

Separate listings will be provided for all laboratory evaluations (hematology, chemistry, prolactin, HbA1c and urinalysis.

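### Protocol and SAP contradict themselves on whether the final HbA1c is taken in subjects who relapse or stop early

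*Protocol*

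**What the plan says.** Seven places give the timing of HbA1c, and they fall into three groups.

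- **Completers only.** Protocol Table 3 footnote c: "HbA1c will be measured only at Baseline, Week 12, and Week 24 (completed subjects only". SAP Appendix 16.1 footnote c repeats it. The protocol synopsis (Safety) agrees: "HbA1c will be measured at Baseline, Week 12 and Completion Week 24 visits".
- **Early termination included.** Protocol 12.1: "HbA1c will be measured at Baseline, Week 12 and at Week 24 Completion or Early Termination visits". SAP Section 12 says the same, and SAP 12.2 has "HbA1c will be measured at the baseline, week 12 and week 24 completion or early termination visits".
- **Silent.** The laboratory table in Protocol 12.1.13: "Hemoglobin A1c (HbA1c) at Baseline, Week 12 and Week 24".

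For haematology, chemistry, urinalysis and prolactin, Protocol 12.1 uses a wider visit description: "Week 24 Completion or Relapse/Early Termination". The synopsis, SAP 12 and SAP 12.2 draw the same contrast between those tests and HbA1c.

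In Table 3 itself, HbA1c sits in the central laboratory row. That row is marked in a single column covering Day 169, Relapse and ET, and only the footnote narrows it.

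The planned analysis in SAP 12.2 comprises descriptive change from baseline, low-normal-high shift tables, and a further summary: "Shift (0.5% change) from baseline will be summarized for HbA1c by visit for each treatment group".

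**The concern.** A site that follows the schedule footnote and a site that follows Section 12.1 would collect different data, and an HbA1c that was never drawn cannot be recovered at analysis. The SAP contradicts itself, so it cannot settle the matter.

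The loss would not be random. Relapse is the primary endpoint, and a subject who relapses is withdrawn from blinded medication, so a completers-only rule removes subjects according to outcome and, if the drug works, more often on placebo. The by-arm shift tables would then compare a minority of placebo subjects with a majority of ecopipam subjects.

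HbA1c is not incidental here. Protocol 5.3.2 and 5.3.3 present the absence of metabolic events as an advantage over D2 antagonists. SAP 16.5 lists raised glucose or HbA1c and metabolic syndrome among the potential adverse events of dopamine antagonists.

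**Working it through.** **Inputs.** Relapse proportions of "65% in the placebo group and 34% in the ecopipam group" for children and adolescents, 49 subjects per arm, hazard ratio 0.4, two-sided alpha 0.05, power 85% and 49 events (Protocol 13.5). No document gives an HbA1c completion rate, a rate of discontinuation without relapse, or an adult relapse rate.

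**1. The plan's own figures.** Freedman's formula gives events = [(1 + 0.4)/(1 − 0.4)]² × (1.960 + 1.036)² = 5.444 × 8.978 = 48.9, so 49. Power at 49 events is Φ(√49 × 0.6/1.4 − 1.960) = Φ(1.040) = 85.1%. Expected events are 49 × 0.65 + 49 × 0.34 = 31.85 + 16.66 = 48.5, and 49/0.495 = 99.0 subjects, against about 98 stated. The planning assumptions are consistent with each other and can be used below. The sample size is not in question.

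**2. Coverage if the footnote is followed and nobody leaves without relapse.** Share with a post-randomization HbA1c = 1 − relapse proportion.

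- Placebo: 1 − 0.65 = 35%; 49 × 0.35 = 17.15, about 17 of 49.
- Ecopipam: 1 − 0.34 = 66%; 49 × 0.66 = 32.34, about 32 of 49.
- Both arms: 17.15 + 32.34 = 49.5 of 98, or 50.5%.

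**3. Sensitivity to other dropout (assumed, 5% to 20%).**

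| Assumed dropout without relapse | As a share of non-relapsers: placebo / ecopipam | As a share of all randomized: placebo / ecopipam |
|---|---|---|
| 5% | 33% / 63% | 30% / 61% |
| 10% | 32% / 59% | 25% / 56% |
| 20% | 28% / 53% | 15% / 46% |

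For example, 0.35 × 0.90 = 0.315 and 0.66 × 0.90 = 0.594; or 0.35 − 0.10 = 0.25 and 0.66 − 0.10 = 0.56. The gap between arms stays at about 25 to 31 percentage points.

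The step 2 figures are therefore approximate ceilings. One thing could raise them slightly: a subject who first meets the relapse criterion at Week 24 itself might count as completed.

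**4. Coverage if the Early Termination wording is followed.** If a Relapse visit counts as Early Termination, coverage is close to 100% in both arms, less those with no such visit. If it does not, the wording recovers only subjects who stop without relapse, the group set to zero in step 2.

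**5. Stopping before Week 12.** Under the footnote, a subject who leaves the open-label period before Week 12, for instance because titration is not tolerated (Protocol 10.5), has a Baseline HbA1c and no on-drug value. This holds whatever the relapse rates are.

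**6. Labelling.** SAP 8.4 assigns Early Termination assessments to the next visit at which that parameter is scheduled. For HbA1c after Week 12, that is Week 24. A sample taken at a Week 13 termination would be tabulated as Week 24.

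**The case against.** The strongest reply has four parts.

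- **The restriction may be deliberate.** The synopsis gives the Relapse/Early Termination visit for the other tests and then limits HbA1c to completion. An HbA1c drawn a week or two after the Week 12 sample adds little. This is plausible, but no passage gives that reason, and Protocol 12.1 and SAP 12 and 12.2 would then be wrong.
- **The contradiction does not account for the whole loss.** A reader might infer that the footnote alone costs about half of the post-randomization values and that the wider text would restore them. The documents do not support that, because the wider HbA1c sentences name Early Termination and not Relapse. Whether relapsers are covered is open even there. This part stands.
- **Metabolic safety is not lost.** A reader might infer that early stoppers go unmonitored. They do not: chemistry, including glucose, cholesterol and triglycerides, and weight are still collected at Relapse/ET and at both follow-up visits. The Week 12 HbA1c is kept under every wording for those who reach it. This stands too and limits the consequence.
- **Taking HbA1c at relapse brings its own bias.** Samples would be earlier in the arm that relapses sooner, and SAP 8.4 would hide this under a Week 24 label. The fix has to deal with that.

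**Conclusion.** The contradiction is real and runs through both documents. It is not the schedule footnote against everything else, since the synopsis sides with the footnote and the SAP is divided.

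Following the footnote would leave a post-randomization HbA1c for at most about 35% of placebo and 66% of ecopipam children and adolescents. These figures rest on the planned paediatric relapse rates and no other dropout. They are not stated in the documents and should not be extended to all randomized subjects, because adults are also randomized and no adult relapse rate is given.

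The loss would differ by arm and be tied to outcome. Its effect is limited to the descriptive HbA1c change and shift tables, and the primary analysis is untouched. This is a minor point, worth correcting because the correction is cheap and an uncollected sample cannot be replaced.

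**What to change.** Make all seven places agree: in the protocol, the synopsis, Table 3 footnote c, Section 12.1 and the laboratory table in 12.1.13; in the SAP, Sections 12 and 12.2 and Appendix 16.1 footnote c. Delete the completed-subjects-only restriction, list HbA1c at the combined Week 24/Relapse/ET visit, and name Relapse explicitly.

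In SAP 12.2, tabulate Relapse/ET values separately from true Week 24 values, or report them with time since randomization, so that the SAP 8.4 rule does not present an early sample as Week 24.

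If the restriction was intended, state the reason, correct Protocol 12.1 and SAP 12 and 12.2, and label the final HbA1c tables as completers only.

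The cost is wording, one assay and one extra table row. Central laboratory tests are already scheduled at the combined visit. Its blood maximum is 8 mL, the same as Baseline, where HbA1c is drawn, against 6 mL at Week 18, where it is not. That is consistent with room for the assay, though it does not prove that one was planned at relapse. The downside is that a value taken soon after Week 12 carries little information.
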